- **Aim 2:** To identify mediators and moderators of CETA's effect on the primary outcome (retention and viral suppression by 12 months). Our primary mediator will be IPV and primary moderator will be partner involvement. *Hypothesis:* Reduction in IPV after CETA will mediate improvement in retention and viral suppression among women who receive CETA; partner involvement in CETA will increase the effect size.
- **Aim 3:** To assess the cost and cost-effectiveness of CETA vs. active control at increasing the proportion of unsuppressed women who have experienced IPV who are retained and virally suppressed by 12 months. *Hypothesis:* CETA will involve additional costs vs. standard of care but with better retention and viral suppression at 12 months, making it cost effective.
- **Aim 4:** To explore the experience of receiving CETA from the perspective of CETA participants post-intervention, including knowledge and skills obtained, acceptability of reporting on and discussing violence, as well as perceptions of the impact of CETA 24 months or more post-intervention. *Hypothesis:* The qualitative exploration will provide an in-depth understanding on the real experiences, perceptions and acceptability of CETA and durability of the intervention.

OVERVIEW OF STUDY DESIGN

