The violence literature encourages intervention with both males and females to effectively address IPV. After a detailed explanation of the intervention, women who consent will be asked if they are willing to include a current male partner in the intervention if they are randomized to the CETA arm. They will be informed that this is not a requirement to be in the study and that they can participate whether or not they want to include their current male partner. We will explain that if the woman is randomized to CETA and a male partner is included, both partners will be invited to participate in CETA *separately*; they would not be counselled together. In our team's experience in Zambia, there were many males interested in participation and who enrolled and remained in CETA treatment throughout. Our qualitative findings indicated that women wanted their partners to join them in treatment and were generally invested in trying to improve the relationship (rather than exit it). We will explain to the woman participant that we will not disclose to the male partner that the woman has reported IPV.

Women who wish to include a partner will be given an information sheet to give to their partner describing the study and inviting them to participate. The information sheet will invite the male to participate in a program that can help improve health and interpersonal relationships and will note that there will be tea/biscuits at the visit. This information sheet that will be given to the male partner will not mention IPV. Those men who are willing to know more about the study and potentially participate will be asked to either attend information sessions at the clinic on a specified time and date or to ring a free study number where they will be given more information about the study. Alternatively, they could complete their contact details and sign the form indicating that they give consent for the study team to contact them. They can then either return the form themselves to a secure designated collection point at the clinic or return it with their partner. Appointments will be made with all those men who indicate they are interested in the program to come to the clinic or meet at alternative secure locations to complete the consent process. The consent will focus on our primary outcome of adherence, and CETA work with the males will focus on increasing healthy behaviors and skill building to support their

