At the clinic, study staff will have a randomization code within the tablet system used for data collection. Following completion of the baseline assessment, the computer will generate the next randomization group. Randomization will be blocked to ensure that roughly equal numbers end up in each arm. The computer will also generate the randomization assignment for the Randomization ID assigned to the patient (and subsequently linked with their Screening ID). Randomization IDs and assignments will be generated *a priori* by a U.S.-based study team member and linked into the computer system. We will inform the participant of their assignment immediately after the baseline assessment. Those participants who are assigned to CETA will then be asked whether they want to invite a partner and if so, will be given the information sheet and forms to be completed and returned by their partner. Because randomization will occur only after the baseline assessment, some subjects may drop out before randomization, which will be tracked.

k. Study Arms: Common Elements Treatment Approach (CETA)

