- Cost and cost-effectiveness: We will estimate the incremental cost-effectiveness of CETA versus active control in achieving the primary study outcome, retained in care and virally suppressed by 12 months, from the provider perspective. If found to be effective, a budget impact analysis will be conducted to estimate the affordability of routine implementation of the intervention at scale.
- Perceptions and acceptability of CETA: Using qualitative focus group discussions and in-depth interviews with both study participants in the treatment arm, CETA providers and healthcare providers. we will also explore the perceptions, acceptability and durability of the intervention, both as a recipient of care and provider and also the feasibility of delivering this intervention which will help inform recommendations for further implementation and scale up of the intervention, which will help inform recommendations for further implementation and scale up of the intervention.

c. Sample Size

Based on the ENHANCE study(85), we estimate that only 40% of those who are unsuppressed will be retained in care and virally suppressed 12 months post-baseline in the control arm. We believe a 20% increase in the percent suppressed and retained between the CETA and control arms would be clinically meaningful. Our primary aim is to analyze the impact of CETA in the full population; however, we have calculated our sample size to ensure our ability to detect differences separately among women who include a partner. With 80% power and 2-sided $\alpha=0.05$, using a chi-squared test for independent proportions our sample size required is 91 per arm (182 total). To have power to detect mediators and moderators (Aim 2), we will increase the sample size to **400 total** with a minimum of 75 women in the CETA arm who include partners (max of 100), which will give us 80% power to detect an absolute 21% difference between arms in women with partners. To get 75 women who include partners in the CETA arm we will have to randomize about 150 women willing to include a partner if randomized to CETA. We will also include at least 75 partners of women, up to 100.

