We will analyze direct effects of CETA on continuous secondary outcomes (e.g., IPV [via SVAWS], mental health [via CES-D and HTQ], and substance use [via ASSIST score]) using linear mixed models. Fixed effects will include treatment arm, time, and arm X time interactions. Random effects will include participant ID to account for repeat measures. We will calculate robust standard errors. The models will estimate the difference in mean symptom change from baseline to each post-assessment between the treatment groups. The difference in mean change will be standardized to calculate Cohen's d effect size.

e. Moderator Analysis

In addition to main effects for the primary and secondary outcomes, we will evaluate the impact of potential moderators (e.g., lack of viral suppression, partner involvement, age, ethnicity, HIV knowledge and attitudes, education, physical health, duration on treatment, presence of side effects, regimen) on suppression and retention and mental health outcomes. An interaction between the moderator and treatment arm will be included in models described above. The interaction term will serve as the coefficient of interest in assessing whether treatment effects varied by levels of the moderator. For the effect of CETA by inclusion of partners we will compare women who included a partner in the CETA arm to those who said they would have included a partner in the control arm. Risk differences will be used to assess effect sizes within moderator levels.

f. Mediator Analysis

We will assess the role of potential mediating variables (IPV, mental health, substance use) on the impact of treatment on our primary outcome to tease out the direct and indirect effects of CETA. Several of the proposed mediators (e.g., interpersonal violence) may reasonably be expected to interact with the treatment arm to impact our primary outcomes. Invalid estimates may occur if this interaction is not considered in the mediator analysis. To allow for the possibility of exposure-mediator interactions, we will use a counterfactual approach and follow methods described by VanderWeele and Vansteelandt(87,88) and Valeri and VanderWeele(89). These methods are appropriate for both

continuous and binary mediators and outcomes and allow for estimating valid controlled direct effects as well as natural direct and indirect effects.

g. Cost Effectiveness Analysis and Budget Impact Analysis

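### The partner-moderator analysis sets CETA women who actually included a partner against controls who only said they would, so the two groups are not randomised counterparts

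*Combined protocol and SAP*

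**What the plan says.** All references are to the combined protocol and SAP.

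- **Objectives, Aim 2:** "Our primary mediator will be IPV and primary moderator will be partner involvement". The hypothesis is directional: involving the partner should enlarge CETA's effect.
- **Study Procedures, Male Partners:** before randomisation, "women who consent will be asked if they are willing to include a current male partner in the intervention if they are randomized" to CETA. The question goes to every consenting woman, so it covers both future arms.
- **Study Procedures, Randomization:** after assignment, "Those participants who are assigned to CETA will then be asked whether they want to invite a partner". Only the CETA arm gets this second question.
- **Male Partners, continued:** the man must then come forward; "Appointments will be made with all those men who indicate they are interested in the program", and consent follows. The Inclusion and Exclusion Criteria section adds his own eligibility conditions, including an unshared phone, literacy, psychiatric criteria and her disclosure of HIV status to him.
- **Data Analysis, Moderator Analysis:** the partner contrast will "compare women who included a partner in the CETA arm to those who said they would have included a partner in the control arm". The arm-by-moderator interaction is the coefficient of interest, and risk differences are reported within moderator levels.
- **Data Analysis, Sample Size:** "To get 75 women who include partners in the CETA arm we will have to randomize about 150 women willing". The subgroup is stated to give 80% power for a 21-point difference.
- **Data Analysis, Primary Analysis:** intention-to-treat is stated for the primary analyses only.

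**The concern.** In the control arm the subgroup is fixed by an answer given before randomisation. In the CETA arm it is fixed by a chain of later events: she confirms the invitation knowing her arm, he responds, he is eligible, and he consents. A willing CETA woman who drops out anywhere along that chain leaves the CETA group. Her control counterpart stays in, because nothing in that arm could remove her. Randomisation therefore does not balance the two groups.

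The section gives no adjustment, principal-stratum method or sensitivity analysis for this contrast. It does not say where willing CETA women without a partner are placed, or women who first declined and later brought one. Nor does it define inclusion for a man who starts and then stops.

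Partner involvement is the one moderator named as primary, and the sample was raised to 400 to support Aim 2. A selection effect in this contrast could be reported as evidence for or against bringing partners into the programme.

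**Working it through.** **1. The plan's own subgroup figures**

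Inputs from the Sample Size section: 75 women per arm, 40% control success, 21-point difference, two-sided 0.05, chi-squared test.

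- Mean proportion = (0.40 + 0.61)/2 = 0.505.
- z = [0.21 × √75 − 1.96 × √(2 × 0.505 × 0.495)] / √(0.40 × 0.60 + 0.61 × 0.39) = (1.819 − 1.386)/0.691 = 0.626.
- Power = 73.4%, against the stated 80%. At a 40% control rate, 80% power for 21 points needs 88 per arm. This is a separate matter to reconcile. It matters here only because 21 points is the natural yardstick for any bias.

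The 150 figure is 2 × 75, which implies that every willing CETA woman brings a partner. With uptake *u* among the willing, the number to randomise is 150/*u*: 167 at 90%, 188 at 80%, 200 at 75%, 250 at 60%, 300 at 50%. The Sample Size section itself says the final number of men could not be confirmed.

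**2. Bias in the partner-stratum risk difference when CETA has no effect**

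Let *g* be the success risk of women who bring a partner minus that of willing women who do not. Neither *u* nor *g* is in the documents, so both are assumed. Assume also that the willing as a whole succeed at 40% and that no unwilling woman later brings a partner.

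- Willing controls: 0.40, a mixture of *u* joiners and (1 − *u*) non-joiners.
- CETA women with a partner: joiners only, with risk 0.40 + (1 − *u*) × *g*.
- Bias = (1 − *u*) × *g*.

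The false-positive rate uses a normal approximation with 75 CETA women and 75/*u* controls. Worked case, *u* = 0.50 and *g* = 0.20: joiners 0.50, bias 0.10, SE = √(0.50 × 0.50/75 + 0.40 × 0.60/150) = 0.0702. The standardised shift is 1.42 and the two-sided rejection rate is 29.6%.

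| Uptake | Gap 10 points: bias, false-positive rate | Gap 20 points: bias, false-positive rate |
|---|---|---|
| 100% | 0, 5.0% | 0, 5.0% |
| 90% | 1 point, 5.2% | 2 points, 5.8% |
| 80% | 2 points, 5.8% | 4 points, 8.2% |
| 60% | 4 points, 8.6% | 8 points, 19.7% |
| 50% | 5 points, 11.0% | 10 points, 29.6% |

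A negative gap reverses the sign of every bias.

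**3. The interaction**

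The table does not measure bias in the interaction, which also depends on the other stratum. Let *w* be the share of women willing at consent. Suppose willing CETA women without a partner are moved to the no-partner stratum. Under no effect, that stratum's risk difference is then off by [w(1 − u)/(w(1 − u) + 1 − w)] × (risk in willing non-joiners − risk in unwilling women). If they are simply dropped, this second term is zero and the interaction carries the partner-stratum bias alone. The plan does not say which applies.

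**4. The same contrast defined at baseline**

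If the stratum is willingness at consent in both arms, each arm holds the same mixture of joiners and non-joiners in expectation. The bias is zero at any uptake and any gap.

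**The case against.** The strongest reply is that the bias is conditional. It needs both incomplete uptake and a prognostic difference, and the documents establish neither. At 90% uptake and a 10-point gap it is 1 point, which hardly moves the error rate. This stands, and it is why the point is that the contrast may be biased.

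A reader might infer that the bias favours CETA, on the view that women whose partners attend have safer relationships and better adherence. The documents do not support a direction. They provide for the possibility that a man's participation raises the woman's risk, and a woman in an ongoing violent relationship could have the worse prognosis. A reader might also take 10 points, about half of 21, as the expected size. It is the extreme corner of an assumed grid.

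A second reply is that Aim 2 asks about involvement, and willingness is a different quantity. That is true, and it is the real cost of the change. But no analysis of actual involvement is protected by randomisation, so that question can only be explored.

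A third reply is that the 150 figure can no longer be acted on. The Data Safety and Monitoring Plan records all one-year follow-ups as complete by March 2025. A total of 400 could also have contained the 200 willing women needed at 75% uptake. Both points stand: what remains useful is the uptake actually achieved.

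None of these replies makes the two groups comparable, and no other section cures the asymmetry.

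**Conclusion.** The concern holds for the Aim 2 partner contrast. The CETA group is selected on a post-randomisation event and the control group on a baseline answer. The partner-stratum risk difference may be biased whenever uptake among willing women is below 100% and joiners differ in prognosis. The interaction may be affected as well, in a way that depends on an unstated allocation rule. Size and direction cannot be known from the documents. The range of 1 to 10 points, between 90% uptake with a 10-point gap and 50% uptake with a 20-point gap, is illustrative and applies to the partner-stratum risk difference only.

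A reader might infer that the trial's randomisation as a whole is compromised. It is not: the primary comparison takes all 400 women by intention-to-treat and does not use partner status.

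**What to change.** - Define the moderator in both arms as the willingness answer given at consent, before randomisation. Fit arm × willingness in all randomised women as assigned, and report the risk difference with its confidence interval in each stratum.
- Keep the comparison by actual partner inclusion as exploratory. Define inclusion, say where willing CETA women without a partner are placed, and state the assumptions.
- Do not use randomisation as an instrument for partner inclusion. CETA women without a partner still receive CETA, so assignment can affect the outcome by another route and the exclusion restriction fails.
- Note that 150 assumed full uptake, and report actual uptake among willing CETA women.
- Date the amendment and label it as made after follow-up. The Safety Review section describes the study as not blinded, and the documents do not say whether moderator results have been seen.

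**Cost.** No new data are needed provided the consent answer was recorded for every woman; the planned control group cannot be formed without it. The estimand changes to the effect of CETA with partner inclusion offered, among willing women, in place of the effect of actual involvement. Power may fall through dilution. With 94 willing women per arm (80% uptake, assumed) and 40% control success, where women with a partner gain 21 points, power is 82.6% if willing women without one also gain 21, 73.4% if they gain 10, and 63.6% if they gain nothing.

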Before any data collection begins all local approval processes required by the Department of Health will be followed; meetings with clinic staff will take place in order to explain the procedures of the study, the risk and benefits, the confidentiality of results, to establish distress protocols and the referral processes that should be followed at the clinic, identify space to conduct the study, and to allow for any questions. Study participants will be enrolled from subjects referred from the HIV clinic by clinic staff. Study staff will work with clinic staff to ensure they refer to us patients they believe meet the screening criteria of HIV-positive, on ART and having an unsuppressed viral load or evidence of defaulting from treatment or missed/late visits but not necessarily around experiences of violence.

c. Recruitment

Recruitment will be from HIV clinics. Initial recruitment will be done by clinic staff (nurses and doctors) who will refer women to study staff whom they believe to be eligible by virtue of being on ART and virally unsuppressed, defaulted from treatment or had missed/late visits. They will describe the study as testing an approach to help those struggling with treatment adherence. Specifically, we will ask clinic staff to refer adult women who have initiated ART and are virally unsuppressed (viral load > 50) or have defaulted from treatment or had a missed or late visit in the last year to a member of our study team. This would be typical knowledge clinic staff has on women. Recruitment materials will not be provided as this may result in increased risk if there is a paper laying around the clinic with criteria. Clinic staff will not ask any questions of these women about experiences of violence beyond what they might otherwise do as part of usual clinical care. During our previous research, this has worked well.

Study staff will speak with any woman who expresses a willingness to learn more about the study. Therefore, potential participants will have no initial contact with study staff unless they express an interest in hearing more about the study. Study staff will be highly trained and will receive specific training in human subject's research and good clinical practice. All referrals happen in person and introductions will occur at standard of care visits.

d. Recruitment process for Focus group discussion and In-depth interviews

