Recruitment of participants for the qualitative phase of the study, will be done in the post intervention period. All those participants who were enrolled into the CETA study and randomized to the CETA treatment arm between 1 January and 31 July 2023 will be contacted via SMS using the contact details they provided, and asked if they are interested in participating in a follow-on discussion to the intervention. Those study participants who can be reached and express an interest in participating will then receive a phone call from the study team member who will explain the additional consent process. The full informed consent process will be completed in person before the FGDs and IDIs.

The recruitment process will adopt a purposive sampling method, as we are only selecting participants from the treatment arm who completed the intervention in 2023, making the sampling population much smaller, so this method will allow us, to maximize on the available population size to gain in-depth insights from the participants. For the recruitment of healthcare providers and CETA providers, they will be contacted and informed about this phase of the study and then asked if they will be interested in participating, informed consent will be conducted before the interview.

e. Screening and Screening Consent

Patients who agree to be referred to a member of our study team will receive a brief consent form only for screening to determine eligibility. This conversation will take place in a private location and include only the study staff and the patient. Potential participants will be counseled that they can refuse to participate in the study and still receive HIV care at the treatment site with no risk to the quality of care they receive. The short consent form will explain what questions participants will be asked, including questions related to IPV, as part of the screening process. All those consenting to be screened will be assigned a unique Screening ID (generated *a priori* by a study team member) and administered a screening questionnaire to confirm the inclusion/exclusion criteria. This will include the Severity of Violence Against Women Scale (SVAWS) physical/sexual violence subscale to assess IPV exposure, which previously been used among women who experienced IPV in South Africa. This is a self-administered tablet-based form. Results of the screening will be documented on a tablet-based screening form

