REDCap or a similar software program requiring secure log-in and access by invitation will be used to create an electronic database to manage any quantitative study data not entered directly into tablets. The database will be used by field staff to double enter data where necessary. Data files will be reviewed by the study team on a monthly basis and queries returned to the site-level staff for response. On a regular basis, the data will be converted to SAS, STATA or SPSS for final cleaning and data analysis. All analytic databases will be password protected with access restricted to the members of the study team.

DATA ANALYSIS

a. Primary Outcome

Our primary outcome is the proportion of participants who are retained and suppressed by 12 months post randomization(34,82). Viral load testing is routinely done at the clinic at 6- and 12-months post ART initiation and every 12 months thereafter. Due to the variability in when viral load testing is done, we will define the primary outcome to be suppression (i.e. a viral load <50 copies/mL) any time up to 18 months. As our primary outcome includes retention, we are not able to contact patients who miss routine viral loads as this would affect attrition. Instead we will use routine clinic data collection (as we have done in the past (83–86)) to determine outcomes. Missing viral loads will be a negative outcome.

b. Secondary Outcomes

- Viral suppression at 3 and 24 months: CETA may have some effects on suppression and retention over the first year on treatment mediated through the increased contact with patients that CETA

entails. It is not clear for how long after the CETA intervention effects will be sustained. Thus, we will look at suppression at 24 months, long after CETA is complete. As our population should be monitored for suppression more frequently than every 12 months, we will also examine suppression within 3 months.

- Attrition at 12 and 24 months - Attrition (the opposite of retention) will be defined as being more than 90 days late for a study visit.
- IPV, mental/behavioral health, alcohol and other substance use: We will measure the effectiveness of CETA in reducing IPV and stress-related problems commonly associated with IPV and HIV, mental health (trauma, depression, anxiety), and alcohol and substance use. We will also assess whether a change in these factors mediates the effectiveness of CETA on the primary outcome.

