Costs will be estimated from the provider perspective over the 12-month study period. Micro costing methods will be used to cost all resources utilized for the care and treatment of the patient during this period, including drugs dispensed, laboratory tests performed, and consultations with clinical staff. This resource utilization will be estimated based on routine patient medical records in addition to study specific patient records. The cost will then be estimated by multiplying the resource usage with the relevant unit costs. In addition to the resources utilized directly by the patient we will estimate costs of infrastructure and shared services including equipment, space, utilities, general supplies and non-clinical staff. These costs will be allocated to the patient using an appropriate allocation factor. Trial specific costs which would not be incurred in routine implementation will be excluded (i.e. screening, informed consent). Unit costs and shared indirect costs will be collected from various sources including national drug tender price lists, state price lists for laboratory and diagnostic tests, national public sector salary banding, site level financial and management reports and our prior HIV costing studies.

Based on the primary outcome, the difference in the cost of producing a patient retained and suppressed by 12 months between arms (total costs of all patients in an arm divided by number achieving primary outcome) as well as the incremental cost effectiveness ratio (ICER) between the study arms (difference in costs divided by difference in effectiveness) will be evaluated. Because cost data are often skewed, and the costs per successful outcome and ICER are ratios of random variables, bootstrapping methods will be used to produce confidence intervals around the cost differences.

If the intervention is found to be effective, we will conduct a budget impact analysis (BIA) to understand the affordability of the intervention based on various possible scale up strategies. This will consider how the intervention may replace (or not) any existing interventions, whether it is likely to change health care utilization and likely intervention uptake. The BIA will take the payer's perspective using a short-term time horizon.

h. Qualitative Data Analysis

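### The cost-effectiveness analysis costs 12 months of care but counts successes to month 18, and does not settle how IPV identification and male-partner sessions are costed

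*Combined protocol and SAP*

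**What the plan says.** All of this is in the combined protocol and SAP.

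- **Cost window** (Data Analysis, g. Cost Effectiveness Analysis and Budget Impact Analysis): "Costs will be estimated from the provider perspective over the 12-month study period".
- **Cost per success** (same section): "total costs of all patients in an arm divided by number achieving primary outcome". The ICER is the between-arm difference in cost over the difference in effectiveness, also based on the primary outcome.
- **Success window** (Data Analysis, a. Primary Outcome): "we will define the primary outcome to be suppression (i.e. a viral load <50 copies/mL) any time up to 18 months". The reason given is that routine viral loads are done at variable times. The cost section and several others still label the outcome as by 12 months.
- **Excluded costs** (section g): "Trial specific costs which would not be incurred in routine implementation will be excluded (i.e. screening, informed consent".
- **Content of the screening** (Study Procedures, e. Screening and Screening Consent): "This will include the Severity of Violence Against Women Scale (SVAWS) physical/sexual violence subscale to assess IPV exposure".
- **IPV questions by referring staff** (Study Procedures, c. Recruitment): "Clinic staff will not ask any questions of these women about experiences of violence beyond what they might otherwise do". Under the active-control heading, usual care for IPV is described as having no formal intervention.
- **Whose resources are costed** (section g): "Micro costing methods will be used to cost all resources utilized for the care and treatment of the patient during this period". Infrastructure and shared services are added and allocated to the patient. Male partners are not mentioned.
- **Male partners** (Data Analysis, c. Sample Size): "We will also include at least 75 partners of women, up to 100". The section on CETA for male partners says that each man is seen individually.

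**The concern.** A cost per success is interpretable only if cost and success refer to the same people, the same intervention and the same period. Here the numerator stops at month 12 and the denominator runs to month 18. A woman whose qualifying viral load falls in month 15 counts as a success, but her care in months 13-15 costs nothing.

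The exclusion rule has a related problem. Its test is whether a cost would arise in routine use, and it lists screening as failing that test. Yet CETA is aimed here at women with recent IPV, and the plan describes no other pre-treatment step that would find them. Finally, partner sessions take place in the CETA arm only, and any benefit from them enters the woman's outcome. If they were left out of the cost, the CETA arm would be credited with an effect that it had not paid for.

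The cost-effectiveness results are Aim 3 and lead to a budget impact analysis for a payer, so the cost base should be that of the programme the payer would fund. The primary efficacy comparison is not affected.

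**Working it through.** The cost section states no figures and the documents give no unit costs, so the check is in resource units rather than rand.

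**Inputs**
- 400 women, 50-50 allocation (Sample Size; Full Consent): 200 per arm.
- Control success 40%; target gain 20%, read as absolute, so 60% with CETA (Sample Size). These rates are stated for 12 months; I assume them for the 18-month count too.
- 50% of screened women eligible, 50% of those enrolled (Sample Size).
- 75-100 male partners (Sample Size); 6-12 sessions per course (Study Arms: CETA).

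Successes: 200 × 0.60 = 120 with CETA, 200 × 0.40 = 80 in control, a difference of 40.

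**Plan's own figure.** Number to screen: 400 / (0.50 × 0.50) = 1600. This reproduces the stated figure.

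**1. Time window**
- Mismatch: 18 - 12 = 6 months, or 6/18 = 33% of the outcome window. This is a share of time, not of money.
- Average cost per success, upper bound with every woman in care throughout: CETA 200 × 12 / 120 = 20 care-months against 200 × 18 / 120 = 30; control 200 × 12 / 80 = 30 against 200 × 18 / 80 = 45. With losses from care the increase is smaller, but it cannot be negative.
- If successes are restricted to month 12 instead, and a share f of successes is first seen after month 12, the 12-month cost over the 18-month count equals (1 - f) times the 12-month cost over the 12-month count: 0.95, 0.90 and 0.80 for f = 5%, 10% and 20% (assumed values).
- ICER, holding the effect at 0.20: change = 6 × (difference in proportion in care, CETA minus control) / 0.20.

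| Difference in care, months 13-18 (assumed) | Change in care-months per additional success |
|---|---|
| +20 points | +6 |
| +10 points | +3 |
| 0 | 0 |
| -5 points | -1.5 |

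If successes are restricted to month 12 instead, the ICER's denominator also changes, up or down according to which arm has more late successes.

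**2. Screening**
- Per randomised woman: 1600 / 400 = 4 screens. Per eligible woman: 1 / 0.50 = 2.
- Per additional success, if charged to CETA only: 4 / 0.20 = 20, or 2 / 0.20 = 10.
- If both arms carry the cost equally, the change in the ICER is 0.
- Both yields cover all the trial criteria, and the first also covers willingness to enrol. Neither is an IPV-positivity rate, so 10 and 20 show scale only.

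**3. Partner sessions**, assuming equal sessions per man and woman
- Women: 200 × 6 = 1200 to 200 × 12 = 2400 sessions. Men: 75 × 6 = 450 to 100 × 12 = 1200.
- Addition: 75/200 = 37.5% to 100/200 = 50%.
- Share of all CETA sessions: 75/275 = 27% to 100/300 = 33%.
- Sessions per additional success: 1200/40 = 30 to 2400/40 = 60 without partners; 1650/40 = 41.25 to 3600/40 = 90 with them.

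**The case against.** **The window.** Month 18 is there only to catch late routine viral loads, and the outcome is labelled by 12 months throughout. CETA lasts about 3 months, so its delivery is fully costed; only later routine care is left out, in both arms. Many successes may come well before month 12, and costing each woman only to her qualifying viral load could lower the cost. All of this limits the size of the problem. It does not remove it: the cost section uses the primary outcome, and the section defining that outcome allows 18 months.

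**The ICER.** A reader might infer that the ICER is biased in CETA's favour. That is not established. Months 13-18 can raise it, lower it or leave it unchanged, and screening cancels if both arms carry it. Nor does the 33% mean that a third of routine care cost is missing.

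**Screening.** The exclusion applies only to costs that would not arise in routine use. Trial screening also checks phone ownership, literacy, psychiatric status and other-study enrolment, which are rightly left out. IPV is assessed again inside CETA, and the budget impact analysis can consider scale-up strategies. This stands against putting a fixed two screens per eligible woman into the base case. It does not answer the point that the plan fails to separate eligibility checks from IPV identification.

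**Partners.** A reader might infer that only the woman's own resources are costed, or that men's sessions are excluded. The documents support neither. Shared and infrastructure costs are included, study-specific records are a cost source, and partner sessions are simply not named. The Sample Size section also says that the final number of men could not be confirmed.

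**Conclusion.** The window mismatch holds as written: 12 months of cost against successes counted over 18. Relative to costing the full outcome window, average cost per success is understated within each arm. The ceiling is 18 rather than 12 routine care-months per woman who stays in care; the amount in money cannot be found without unit costs and retention data. The direction of the effect on the ICER is open.

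The screening point holds in a narrower form. The named exclusion takes in the only IPV detection step before treatment that the plan describes, and the trial-only part is not marked off. Its weight depends on an IPV yield that the documents do not give and on whether identification is charged to CETA alone.

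On partners, the finding is silence, not exclusion. It matters because, of the three items, this is the one whose omission would clearly lower the ICER, there being no men in the control arm. The 38-50% addition rests on the target number of men and equal sessions per person.

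**What to change.** 1. **Align the windows.** In the base case, measure costs to month 18, or restrict successes to month 12 for the cost analysis. Show the 12-month costing as a sensitivity analysis, and use one label for the outcome in the cost section.
2. **Narrow the screening exclusion** to informed consent and trial-eligibility steps. Add a scenario that charges IPV identification to the CETA strategy, with the yield varied over a stated range. Carry that scenario into the budget impact analysis.
3. **State that male-partner CETA sessions are costed in the CETA arm**, using the sessions actually delivered.

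Cost: a few sentences in the SAP and some extra costing work. Under Data Sources and Management, resource use is taken from clinic records up to 24 months, attendance at CETA sessions is recorded, and partner completion is linked to the woman's data. No new patient contact is needed. The possible downside is a less favourable cost figure.
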